1.3 PATIENT AND PUBLIC INVOLVEMENT (PPI)

The Language Explorer application is being developed with funding from the NIHR i4i programme. The proposed project covered by this ethics application is one stream of work within the awarded grant. In the development of the original grant PPI representation was embedded at all points. This has been maintained in the development of the proposed work covered by this application. Currently, the tool is being used by parents and carers with their children in a citizen science activity which will lead to a normative dataset and provide information on functioning of the tool which will be used to make further developments. Children with language impairments were also supported to complete the app in schools in Bristol and Hackney.

The plans for the clinical evaluation, as described in this protocol, have been reviewed by our PPI partner, the CEO of the Association For All Speech Impaired Children (AFASIC), and amendments made in light of her comments. The protocol has also been reviewed and agreed by the local PIs.

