At the start of the assessment, the SLT will take assent from the study child using the 'Child Assent Form' (Appendix J). If the child is too young or unable to tick the boxes themselves, or the assessment is taking place remotely, the SLT will initial the boxes. If a child is felt not to have provided assent, the assessment session will not go ahead.

Eligibility criteria for children

Inclusion criteria:

- Children aged between 4;0 and 7;11 years
- Children who speak and are exposed to only English in the home
- Children who have been identified by a speech and language therapist as having DLD or suspected DLD. (DLD is defined here as having moderate to severe language difficulties, not associated with other conditions but which is likely to affect their

functioning in school/preschool and likely to persist – based on the clinical judgment of a SLT)

- Case histories that are unremarkable in terms of birth, overall development and general health

Exclusion criteria

- Children with history of significant hearing problems (e.g. sensori-neural hearing loss or use of hearing aids in the case of severe and recurrent otitis media)
- Evidence of structural or neurological disorders (e.g. cleft palate, cerebral palsy, autism)
- Children with significant speech difficulties which impact their intelligibility

Parents/Carers

The 'Consent Form (Parents/Carers)' (Appendix H) seeks consent for the parent to participate in a semi-structured telephone interview carried out by the study team following their child's attendance at the Language Explorer Assessment Clinic. During the interview they will be asked about the experience of their child using the Language Explorer. Consent for this will be an optional element; the parent can consent for their child to participate in the study but choose not to consent to themselves being interviewed. Parents/carers recruited to the study will be assigned a separate but related ID number to that of their child. Processes for maintaining security and confidentiality of the parents/carers identifying information will be the same as that for the child described above.

Parent/Carer eligibility:

- Parent/carer of a child meeting the inclusion criteria for this study

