4. DESIGN

4.1 TYPE OF STUDY:

This study will use mixed methods. Quantitative assessment data will be collected from the children via a novel tool (the Language Explorer app – the tool under investigation in this clinical evaluation, described below), one of two standardised assessments depending on age of the child (Clinical Evaluation of Language Fundamentals Preschool - Second Edition (CELF-Preschool 2 UK, Appendix K ‘CELF-Preschool 2 UK Form) or the Q-Interactive version of the Clinical Evaluation of Language Fundamentals – Fifth Edition (CELF-5 UK, Appendix L ‘CELF-5 UK Form’) i.e. the ‘CELF Assessments’, and a ‘Clinical Judgement Form’ (Appendix M), completed by SLTs immediately following the Language Explorer assessment appointment.

Children’s performance on the Language Explorer app will be compared with that of a normative sample, collected from 600 children in 6 month age bands from across the UK in a separate Citizen Science workstream (ethics approval for this has been granted by the University of Bristol and data collection is in process). This analysis will enable us to determine whether the app can be used to distinguish children with DLD from those who are typically developing.

Children’s performance on the app will also be compared with scores on subtests of the standardised CELF assessments and also the SLT clinical judgement of the child’s needs. This analysis will enable us to determine whether the Language Explorer can be used to distinguish different patterns of performance in children with DLD which could be used to provide guidance on clinical need and management to speech and language therapy services in the future.

The sample size will be too small to determine sensitivity and specificity and predictive values but instead will provide exploratory data to determine whether a fully powered study to determine validity is required.

Qualitative data will be collected from SLTs and parents/carers through semi-structured interviews to determine the value of the app to clinicians and service users and to identify any modifications which might be needed to improve its functioning and appeal.

4.2 DATA COLLECTION:

Four types of data will be collected and analysed:

- 1) Language Explorer transcription and analysis scores (screenshots in Appendix N)
- 2) Clinical Evaluation of Language Fundamentals (specifically CELF- Preschool 2 UK and CELF-5 UK) assessment forms and subtest scores (Appendix K and L).
- 3) SLT Clinical Judgement Form

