The SLT carrying out the assessment sessions will follow exactly the coronavirus infection control protocols for carrying out assessments in person in a clinical setting, as specified by their service. At the start of the assessment, the SLT will take assent and confirm eligibility and consent as described above. The SLT will then open the Language Explorer app and use the child's unique study ID number as their username and use the app to collect a language sample, as described for the remote setting. The SLT service will have been provided with iPads with Language Explorer already loaded. Once data collection for the Language Explorer app is complete, the SLT will begin the assessment on the Clinical Evaluation of Language Fundamentals assessment as described below.

2) *The CELF Assessments and Clinical Judgement Form*

Remote (ages 6 years 0 months to 7 years 11 months):

When the child has completed all tasks of the Language Explorer app, assessed using the Q-Interactive version of the CELF-5, completing these tasks in order: Word Structure (Expressive Core), Recalling Sentences (Expressive Core), Formulated Sentences (Expressive Core), Understanding Spoken Paragraphs. The child's direct involvement in data collection ceases at this point and the appointment can be concluded.

In person (ages 4 years 0 months to 5 years 11 months):

When the child has completed all tasks of the Language Explorer app, the child will be assessed by the SLT using the CELF-Pre-school 2 assessment. The subtests of the CELF assessments will be carried out in the order: Word Structure (Expressive Core) followed by Recalling Sentences (Expressive).

The SLT will be able to carry out any additional assessments that s/he would typically use to inform clinical judgement of the child's language competence but data from these will not be collected by the study team or used in the research.

Following completion of the CELF assessments carried out by the SLT, the SLT will score the CELF assessment for raw scores, sum of subtest scaled scores, standard scores, percentile ranks and confidence intervals, following the scoring guidelines in the manuals. Once the scoring has been carried out, the SLT will complete the Clinical Judgement form. Alternatively, the SLT who has completed the Language Explorer and CELF assessments can ask another SLT in the team who is more familiar with the child to complete the Clinical Judgement Form.

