6. DATA ANALYSIS

Descriptive statistics for the Language Explorer tasks and the CELF assessment scores will be generated.

Initial qualitative analysis of the Language Explorer automatic language analysis report will be carried out to determine scores for outputs obtained in the report (e.g. mean length of utterance, types of words used e.g. nouns, verbs, adjectives and grammatical markers used e.g. regular plural s, possessive s and past tense -ed). Performance on these sub-scores for the clinical sample will be compared with those obtained from children assessed in the separate Citizen Science workstream. Using a known groups methodology, we will determine if the children with DLD can be distinguished from children with typically developing language based on scores on the Language Explorer.

Further analysis will use Language Explorer scores in a correlation analysis with the CELF assessment sub-scores to determine the strength of the relationship between the sub-scores on the Language Explorer and children's performance on the CELF assessment subtests and core scores (also continuous scores).

Cluster analysis of the sub-scores from the Language Explorer app will be carried out to determine if patterns of performance can be observed. Any patterns identified will be

considered against the information on areas of clinical need identified on the Clinical Judgement form and sub-score performance on the CELF.

Transcripts of the SLT and parent/carer interviews will be analysed using thematic analysis, following the process outlined by Braun and Clarke (2006). After reviewing the data, the team will identify initial codes representing themes that arose during the interviews. These initial codes will be discussed through meetings with members of the study team and a common set of initial codes will be agreed upon, named, and defined. Each researcher will apply these codes to their data, all the while remaining open to new codes. Through discussions, these initial codes will be subsequently further refined and re-named as necessary and will then be grouped into sub-themes and cross-checked to ensure that they capture the meanings in the data.

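### Objective 1 is at risk of bias: a normative sample stands in for typically developing children, and at ages 4–5 case status is confounded with who runs the app

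*Protocol*

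**What the plan says.** Section 3 sets objective 1 as telling children with DLD apart from those with typical language. Section 4.1 names the only comparator: app performance is to be "compared with that of a normative sample, collected from 600 children in 6 month age bands from across the UK". The sample comes from a separate Citizen Science workstream with its own ethics approval. Section 4.1 expects this comparison to "determine whether the app can be used to distinguish children with DLD from those who are typically developing".

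Section 6 repeats the comparison without restriction: "Performance on these sub-scores for the clinical sample will be compared with those obtained from children assessed in the separate Citizen Science workstream". It then says of the known-groups analysis that "we will determine if the children with DLD can be distinguished from children with typically developing language".

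Cases face several filters in Section 2.2. One is "Children who speak and are exposed to only English in the home"; others cover case history, hearing, structural or neurological disorder, and intelligibility.

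On administration, Section 1.3 says that "the tool is being used by parents and carers with their children in a citizen science activity" and then adds: "Children with language impairments were also supported to complete the app in schools in Bristol and Hackney". Under Section 4.3, cases aged 4;0–5;11 are tested in person by a speech and language therapist (SLT): "The SLT service will have been provided with iPads with Language Explorer already loaded". For cases aged 6;0–7;11 the parent runs the app remotely while an SLT observes. Section 4.2 uses data from all children for the first aim.

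On transcripts, Section 4.2 and item (3) of Section 4.3 score the SLT-corrected transcript. The last bullet of the flowchart closing Section 4.3 says the report comes from the automatic transcript. How norm transcripts are processed is not described.

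**The concern.** A known-groups comparison needs known status in both groups. The protocol fixes it for the cases only and equates normative with typically developing for the controls. A normative sample may properly include children with language difficulties, and Section 1.1 says that more than half of children with DLD go unidentified. Affected children among the controls would shrink the observed separation. Home language and hearing could also differ between the groups for reasons unrelated to DLD.

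At ages 4–5, all cases are SLT-run and the norm children used the app with parents or carers. A group difference in that age band cannot be separated from a difference in administration, and the protocol describes neither stratification nor adjustment.

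Two smaller matters add to this. Some children with language impairments in Bristol and Hackney, two of the three recruiting areas, have already completed the app, and Section 2.2 has no rule on prior use. Mean length of utterance and grammatical-marker scores also depend directly on whether the transcript was corrected.

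What is at stake is the decision in Section 4.1 on whether a fully powered validity study is required. A larger sample would cure neither problem.

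**Working it through.** The protocol gives no effect size, SD, power or sample-size calculation for objective 1, so there is no stated figure to reproduce.

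**Inputs from the protocol**
- Cases: 3 sites (Section 2.1) × 20 children (Section 4.3) = 60.
- Comparator: 600 children in 6-month bands (Section 4.1).
- Delayed language: about 10% in the early preschool years (Section 1.1). This is not a DLD rate at ages 4–7 and is used only as the upper end of a range.

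**Assumptions**
- True separation d = 0.8, 1.0 or 1.5 SD.
- Share of affected controls c = 5% or 10%, each with the full case deficit.
- Mode effect m = ±0.2 or ±0.3 SD, where positive m enlarges the contrast.
- Even age split: 30 cases and 300 controls aged 4–5. If the bands cover 4;0–7;11, there are 8 bands of 600/8 = 75, and 4 × 75 = 300.

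**Step 1: contamination.** Typical controls are N(0,1), affected controls and cases N(−d,1).
- Observed raw difference = d(1−c).
- Comparator variance V = 1 + c(1−c)d².
- Pooled SD = √[(59×1 + 599×V)/658].

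For d = 1.0 and c = 10%: difference 0.90; V = 1 + 0.09 = 1.09; pooled SD = √(711.91/658) = 1.040; standardised difference 0.90/1.040 = 0.865.

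| True d | c = 5% | c = 10% |
|---|---|---|
| 0.8 | 0.75 | 0.70 |
| 1.0 | 0.93 | 0.87 |
| 1.5 | 1.36 | 1.24 |

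The loss is about 7% to 13.5% at d = 1.0 and about 9% to 17% at d = 1.5. It is always towards no difference. In AUC terms at d = 1.5, (1−c)Φ(d/√2) + 0.5c falls from 0.86 to 0.84 (c = 5%) or 0.82 (c = 10%).

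**Step 2: mode of administration.** In the 4–5 stratum the expected difference is d + m. Overall it is d + 0.5m if half the cases are 4–5. With d = 1.0 and m = ±0.3, the stratum result is 0.7 to 1.3 and the overall result 0.85 to 1.15.

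If there were no true difference, the standard error for 30 versus 300 is √(1/30 + 1/300) = 0.191. The chance that mode alone gives two-sided p < 0.05 is about Φ(0.2/0.191 − 1.96) = 18% for m = 0.2, and 35% for m = 0.3.

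**Step 3: passages side by side**
- *Comparator label:* normative and unrestricted where it is defined (Section 4.1); typically developing where the conclusion is drawn (Sections 4.1 and 6). No criterion links the two.
- *Administration:* parents or carers for the norms (Section 1.3); SLT for cases aged 4–5 and parent with SLT observing for cases aged 6–7 (Section 4.3). The older stratum is closer to the norms but not identical.
- *Scored transcript:* corrected (Section 4.3, item 3) against automatic (flowchart). These conflict.

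**The case against.** The Citizen Science sample belongs to another workstream whose protocol is not shown, and its eligibility rules may already be adequate. A reader might infer that the 600 are unrestricted; silence in this protocol does not show that. What stands is that this protocol draws the typically developing conclusion without stating or cross-referencing a criterion.

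A reader might also infer that the school-tested children with language impairments are among the 600. Section 1.3 does not say so: it links the normative dataset to the parent-and-carer activity and mentions the school children separately. Nor is it shown that any of them will be recruited as cases, or that prior exposure raised anyone's score; no numbers, dates or overlap are given. Both points call for confirmation.

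The app standardises much of the delivery, with a narrated story, automatic picture changes and recorded sentences, so a mode effect may be small. That is plausible, but its size and sign cannot be settled from the protocol.

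The contamination figures lean high. The 10% is an early-preschool rate, Section 1.1 notes that some children progress spontaneously, and giving every affected control the full case deficit is severe. Contamination also works against the app and cannot create a false positive. All of this stands and limits the size of the point.

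Finally, Section 4.1 calls the data exploratory and disclaims sensitivity, specificity and predictive values. Losses expressed in those terms would be beside the point, and the AUC figures are illustrative only.

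**Conclusion.** The objective 1 contrast is at risk of bias. The stronger statement, that it is biased, goes beyond the documents, because the comparator's composition is unseen and the mode effect is unmeasured.

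Two things are established from the protocol's text: the comparator is not shown to earn the label used in the conclusion, and at ages 4;0–5;11 case status coincides with mode of administration. Contamination would attenuate the contrast modestly, by roughly 7% to 17% across d = 1.0 to 1.5 and 5–10% affected controls. A mode effect would pass in full into the 4–5 result, in either direction. Apart from the counts of 60 and 600, every input to these figures is assumed.

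Severity is should-fix: the study is exploratory, but its result feeds the decision on a validity study, and the remedies need no new data collection.

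**What to change.** Amend Sections 4.1 and 6, with a line in Section 2.2 or 6 for item 2.

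1. For the known-groups analysis, restrict the comparator to norm children with no recorded language concern who meet the study's non-DLD criteria, including English only at home. Confirm that the school-supported records are not in it. If the norm data hold no such flags, call the comparator population norms and do not conclude about typically developing children. Unidentified DLD would remain even after restriction, and the report should say so.
2. Exclude clinical-sample children who have already used Language Explorer, or flag them and remove them in a sensitivity analysis.
3. Report the contrast separately for ages 4–5 (SLT-run) and 6–7 (parent-run with an SLT observing), beside the overall result. State the mode confounding as a limit on the 4–5 result without discarding that stratum.
4. Score both groups from the same type of transcript, and reconcile item (3) of Section 4.3 with the flowchart.

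The cost is a few lines of text, somewhat fewer than 600 controls, and less precise stratum estimates (about 30 cases each if ages split evenly, which the protocol does not fix).

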To ensure robustness, the scoring of the CELF assessments, scoring will be repeated by the study team on receipt of the forms to the study team at BSLTRU. Any subtests that were discontinued outside of the discontinuation rules described in the CELF manuals will be discarded.

(3) Correcting the Language Explorer automatic transcript

After the assessment session (either remote or in person in the clinical setting, after the CELF assessment has been completed), the SLT will access the Language Explorer app recording and automatic transcript for the child. (This will be available on the app for those children who have been assessed in person in a clinical setting. For those assessed remotely, this will be made available by Therapy Box to the SLT). This should take place as soon as possible after the assessment session but within a maximum of 3 days. S/he will correct the transcription as necessary, consistent with the usual procedures for the tool. The corrected transcription will then be automatically collected via the app and transferred to a secure AWS server. This will require a Wi-Fi connection. If this is not available in the clinic where the Language Explorer Assessment takes place, the SLT will go to an NHS setting where there is a Wi-Fi connection and initiate the transfer there within one week of receiving the transcript for correction. In the meantime, the device holding the data will be stored in a secure setting. The audio recording and transcription will also be securely transferred to BSLTRU so that the study team can measure inter-rater reliability between the SLT checked transcriptions and those transcriptions corrected by the study team. A proportion (20%) of transcripts will also

be transcribed twice by the same transcriber from the study team at BSLTRU to measure intra-rater reliability of the corrected transcription process.

Once the corrected transcript data has been received at Therapy Box offices, a report of scores from the automatic analysis of the corrected transcription will be generated. This report will be made available to the SLT and to the study team at BSLTRU by the app developers Therapy Box.

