- Local site PI asks SLTs to identify children who fulfil eligibility criteria from their caseloads and from recently discharged cases
- SLTs send recruitment packs (prepared by the study team at BSLTRU) to parents/carers of eligible children in the post or by email
- SLTs contacts by phone or email if no response received within two weeks
- If parents/carers have any concerns/questions, details of who to contact from the study team are available in the Participant Information Sheet

RECRUITMENT

- Parent/carer returns consent forms to local site PI in prepaid envelopes included in recruitment packs.
- Parent/carer and child are allocated unique study IDs by the local site PI, from a list provided by the study team at BSLTRU
- Parent/carer is contacted by local site PI or a SLT participating in the study to arrange a suitable time for a remote or clinic based Language Explorer assessment appointment
- All consent forms copied for local site and originals sent to BSLTRU

LANGUAGE EXPLORER ASSESSMENT APPOINTMENT

carried out by a GCP trained SLT either remotely or in person in a clinical setting

Remote (6;0 – 7;11):

- Prior to appointment, SLT provides information to parent/carer for download of the Language Explorer app onto a suitable device.
- SLT takes assent from the child and confirms eligibility at the start of the appointment
- SLT asks parent/carer to open Language Explorer app
- SLT provides parent/carer with unique study ID number to use as username on app
- Parent/carer uses app with child (minimum data collection = story retell task)
- SLT observes process
- SLT completes subtests on CELF assessment
- Appointment ends
- SLT scores CELF

Clinical Setting (4;0 – 5;11):

- SLT takes assent from the child and confirms eligibility
- SLT opens Language Explorer on Ipad provided by app developers
- SLT uses unique study ID number for username on Language Explorer app
- SLT uses app with child (minimum data collection = story retell task)
- SLT completes subtests on CELF assessment
- Appointment ends
- SLT scores CELF

After the assessment appointment:

- SLT completes Clinical Judgement Form – or asks colleague who knows child better to do this
- SLT accesses Language Explorer automatic transcript and corrects it (App developers Therapy Box will provide access to the automatic transcript for those which have been carried out remotely)
- SLT ensures all study documentation is labelled only with child's unique study ID and no identifying information

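### The story-retell transcript is corrected by the assessing therapist, unmasked to the CELF, so the aim 2 comparisons risk review bias, and the protocol conflicts on which transcript is scored

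*Protocol*

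**What the plan says.** Protocol section 4.3 (3) fixes when the transcript is corrected, in both settings: "After the assessment session (either remote or in person in the clinical setting, after the CELF assessment has been completed), the SLT will access" the recording and automatic transcript. On timing it adds: "This should take place as soon as possible after the assessment session but within a maximum of 3 days". On method it says only: "S/he will correct the transcription as necessary, consistent with the usual procedures for the tool". No masking is mentioned.

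Section 4.3 (2) gives CELF scoring to the same SLT: "Following completion of the CELF assessments carried out by the SLT, the SLT will score the CELF assessment for raw scores". It continues: "Once the scoring has been carried out, the SLT will complete the Clinical Judgement form", with the option of asking a colleague who knows the child better to fill in the form. In the flowchart at the end of section 4.3, CELF scoring closes the appointment block. The post-appointment block then lists the Clinical Judgement Form, followed by: "SLT accesses Language Explorer automatic transcript and corrects it".

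Section 4.2 (Story Re-Tell) and section 4.3 (3) both have the app's analysis run on the corrected transcript. The last item of the flowchart has the report produced from the automatic transcript instead.

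Section 6 then plans a "correlation analysis with the CELF assessment sub-scores", and sets any clusters found in the Language Explorer sub-scores against the form and the CELF.

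**The concern.** A test that is being validated should be read without knowledge of the measure it will be compared with. Here the manual step in the new test is done by someone who has just heard the child answer the CELF items and, by the flowchart, has scored them. The outputs named in section 6 include utterance length and small grammatical endings such as plural, possessive and past-tense markers. Whether an ending is credited can depend on a faint sound in a young child's recording. An SLT who has just watched the child fail or pass CELF Word Structure has an expectation about that sound. If unclear cases are settled in line with the expectation, the story-retell sub-scores move towards the CELF and the form, and agreement looks stronger than the tool alone would give.

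At stake is aim 2, the link between Language Explorer patterns and the CELF and clinical judgement. Section 4.1 says the study's exploratory data will inform whether a fully powered validity study is required. Inflated agreement would feed into that decision.

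**Working it through.** The protocol states no correlation, power or effect size, so there is no figure to reproduce. The check is a reading of the order of events, followed by an illustration of size.

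**Order of events and flow of data**

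1. CELF given before correction: explicit in section 4.3 (3), "after the CELF assessment has been completed", for remote and in-person sessions.
2. CELF scored, and form completed, before correction: this follows from the flowchart order. Two passages support it. Section 4.1 places the form straight after the appointment, and section 4.3 (2) places scoring before the form, while correction may wait up to 3 days. Section 4.3 (3) itself does not state it.
3. Corrector masked: not stated anywhere.
4. Correction enters the score: yes under sections 4.2 and 4.3 (3); no if the last flowchart item governs. Section 5 lists the corrected story-retell transcript among the study data but does not settle which version is analysed.
5. Tasks affected: story retell only. Section 4.2 describes comprehension as a count of picture choices and sentence repetition as a percentage calculated by the app, with no SLT correction for either. Story retell is, however, the minimum task for a child to be analysed (section 4.3 (1)), so every analysed child has an affected score.
6. Safeguards: the study team also corrects transcripts, for inter-rater reliability; 20% are transcribed twice by one team member; and the team re-scores the CELF (all section 4.3). Nothing says the team's correction is the version analysed, or that the team member making it has not seen the CELF.

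**Illustration of size (assumed drift)**

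Let X be the standardised unbiased Language Explorer score, C the standardised CELF score and r their true correlation. Suppose correction changes X to X + λC. Then

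observed r = (r + λ) / √(1 + 2rλ + λ²).

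- r = 0.50, λ = 0.05: 0.55 / √1.0525 = 0.54
- r = 0.50, λ = 0.10: 0.60 / √1.11 = 0.57
- r = 0.50, λ = 0.20: 0.70 / √1.24 = 0.63
- r = 0.30, λ = 0.05: 0.35 / √1.0325 = 0.34
- r = 0.30, λ = 0.10: 0.40 / √1.07 = 0.39
- r = 0.30, λ = 0.20: 0.50 / √1.16 = 0.46

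With λ = 0 nothing changes.

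**Could the data reveal such a shift?**

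Section 4.3 (1) gives 20 children at each of three sites, so n = 3 × 20 = 60. The Fisher interval is tanh(atanh r ± 1.96/√(n − 3)).

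- n = 60, r = 0.50: 0.549 ± 0.260, giving 0.28 to 0.67
- n = 30, r = 0.50 (assuming an even split between the two CELF versions): 0.549 ± 0.377, giving 0.17 to 0.73

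Each illustrated shift from 0.50 lies inside both intervals, so it could not be recognised from the correlation alone.

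**The case against.** The case for the plan has substance. The SLT corrects with the recording to hand, follows the tool's usual procedure, and was present or observing when the child spoke; section 4.3 (1) gives help with transcription as a reason for observing. Inter-rater agreement with the study team is measured, and the CELF is re-scored centrally. The study calls itself exploratory. Section 6 begins the search for patterns by clustering the Language Explorer scores themselves, and uses the CELF and form only afterwards. An analysis plan that is not shown might name the transcript to be analysed.

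These points limit the concern but do not remove it. Audio reduces discretion without ending it, and a reliability coefficient does not take a directional shift out of the scores that are analysed.

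A reader might infer more than the text supports:

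- That the Language Explorer score as a whole is contaminated. Only story retell is described as corrected. Sentence repetition, the closest counterpart to CELF Recalling Sentences, is scored by the app.
- That the child's treating therapist does the correcting. The text supports only the assessing SLT and allows that a colleague may know the child better.
- That prior CELF scoring is a stated rule. It rests on flowchart order; prior administration is what is explicit.
- That the scores have been shown to depend on the CELF. Lack of masking creates a risk, and the drift weights above have no anchor in the protocol.

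**Conclusion.** The concern holds for story retell. The assessing SLT, unmasked to a CELF just given and by the flowchart already scored, makes the manual correction from which sections 4.2 and 4.3 (3) derive the story-retell sub-scores. The CELF correlations and the comparison with the Clinical Judgement Form therefore carry a risk of review bias. Its direction is probably upward, because knowledge of the CELF would tend to pull unclear decisions towards it. Its size is unknown and may be zero; the values of 0.57 and 0.63 for a true 0.50 rest entirely on assumed weights of 0.1 and 0.2.

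The conclusion depends on the corrected transcript being the one scored. If the last flowchart item governs, the SLT's correction does not enter the report and this route to bias closes. That conflict is a defect in its own right. The exploratory purpose lowers the stakes, but a cheap remedy is at hand and the change should be made.

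**What to change.** 1. Reconcile sections 4.2 and 4.3 (3) with the last flowchart item, and state which transcript generates the analysed scores.
2. For the CELF correlations and the Clinical Judgement Form comparison, also run the automated analysis on the study team's corrected transcripts. These should be made from the audio by a team member who has not seen that child's CELF or form. Report the results beside those from the SLT-corrected transcript, labelled as used in practice. A gap between the two shows how far the findings depend on who corrected.

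The cost is one further automated run by the developer, and a division of work so that different existing team members correct the transcript and re-score the CELF for a given child. Alternatively, one person can correct the transcript before opening the CELF form. This assumes the team corrects every child's transcript. Section 4.3 (3) gives no fraction for the inter-rater check (the 20% refers to repeat transcription), so if only a subset was meant, the extra correction time is an added cost.

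Moving the SLT's own correction ahead of CELF scoring would not do the same job, since the SLT has already heard every CELF response.
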